11.3 Study Duration/End of Study

Each subject is expected to complete the study, including all FU and Survival visits, within approximately 132 days. The end of study is when the last visit of the last subject occurs.

11.4 Number of Subjects and Centers

The study will be conducted at approximately 30 sites globally. Approximately 90 subjects are planned to be screened to randomize a total of approximately 60 subjects (30 subjects per group)

into one of the two treatment groups of the study (voriconazole and SCY-078 or voriconazole and SCY-078 placebo).

12.0 Study Population

12.1 Inclusion Criteria

Subjects must fulfill all of the following criteria to be eligible for study admission:

- 1. Subject is a male or female adult ≥18 years of age on the day the study informed consent form (ICF) is signed.
- 2. Subject has a probable or proven IPA based on the protocol-specified criteria (Section 22.3) that requires antifungal treatment.

Note: Subjects with possible IPA may enter the screening phase of the study but will only be randomized after meeting criteria for probable or proven IPA

- 3. Subject has a result of a serum GMI from a sample obtained within the 96 hours preceding enrollment into the study (Baseline/Treatment Day 1).
- 4. Subject has one of the following:
 - a. has a diagnosis of a hematological malignancy or a myelodysplastic syndrome or aplastic anemia or has undergone a hematopoietic cell transplantation OR
 - b. who either recently resolved or ongoing neutropenia (neutropenia defined as absolute neutrophil count < $0.5 \ge 10^{9}$ /L [< 500/mm3] for > 10 days), temporally related to the onset of fungal disease **OR**
 - c. who received treatment with other recognized T-cell immunosuppressants (such as cyclosporine, tacrolimus, monoclonal antibodies or nucleoside analogs) during the past 90 days including solid organ transplant patients **OR**
 - d. with inherited severe immunodeficiency (e.g. chronic granulomatous disease, severe combined immunodeficiency).
- 5. Subject has not received more than 4 days (96 hours) of prior mold-active antifungal therapy for the treatment of the IPA episode in the 7 days preceding enrollment into the study (Baseline/Treatment Day 1). However, subjects who have received more than 4 days but less than 7 days of prior mold-active antifungal therapy for the treatment of the IPA episode in the 7 days preceding enrollment into the study may be enrolled but will require approval from the study medical monitor, who will evaluate each subject on a case-by-case basis.
- 6. For subjects who were receiving antifungal prophylaxis, the IPA episode would, in the investigator's judgement, be adequately treated with voriconazole .
- 7. Subject is able to tolerate medication orally or through a nasogastric (NG) tube or percutaneous endoscopic gastrostomy (PEG) tube.
- 8. Subject is not pregnant and is highly unlikely to become pregnant or to impregnate a partner since he/she meets at least one of the following criteria:

- a. Subject is a female subject who is not of reproductive potential and is eligible without requiring the use of contraception. A female subject who is not of reproductive potential is defined as one who: (1) has reached natural menopause (defined as 6 months of spontaneous amenorrhea with serum follicle-stimulating hormone levels in the postmenopausal range as determined by the local laboratory, or 12 months of spontaneous amenorrhea); (2) is 6 weeks' post-surgical bilateral oophorectomy or hysterectomy; or (3) has undergone bilateral tubal ligation. Spontaneous amenorrhea (i.e., anorexia nervosa).
- b. Subject is a male subject who is not of reproductive potential and is eligible without requiring the use of contraception. A male subject who is not of reproductive potential is defined as one whom has undergone a successful vasectomy. A successful vasectomy is defined as (1) microscopic documentation of azoospermia, or (2) a vasectomy more than 2 years ago with no resultant pregnancy despite sexual activity post vasectomy.
- c. Subject is a male or female subject who is of reproductive potential, is not pregnant or nursing, and agrees to remain abstinent or use (or have his/her partner use) 2 acceptable methods of contraception starting from the time of consent through 28 days after the completion of study therapy. Acceptable methods of birth control are intrauterine device, condom and highly effective hormonal contraceptives.

Note: Participating females of childbearing potential must have a negative urine or serum pregnancy test (β -human chorionic gonadotropin [β -hCG]) at Screening and prior to enrollment (Baseline/Treatment Day 1) (performed by the site's local laboratory).

- 9. Subject and/or legal representative is/are able to understand and sign a written ICF, which must be obtained prior to treatment and any study-related procedures.
- 10. Subject and/or legal representative is able to understand and sign a consent or authorization form, which shall permit the use, disclosure and transfer of the subject's personal health information (e.g., in the US, a Health Information Portability and Accountability Act Authorization form).
- 11. Subject and/or legal representative is able to understand and follow all study-related procedures including study drug administration.
- 12. Subject is willing and able to comply with the study restrictions and participate for the full length of the study.

12.2 Exclusion Criteria

A subject will be excluded from participation in the study if he or she meets any of the following exclusion criteria:

1. Subject has a fungal disease with central nervous system involvement suspected at Screening.

- 2. Subject is receiving, has received or anticipates to be receiving concomitant medications that are listed in the prohibited medication list (Section 22.1) within the specified washout periods.
- 3. Subject has a Karnofsky score <20.
- 4. Subject is expected to die from a non-infectious cause within 30 days from the day the study ICF is signed.
- 5. Subject is under mechanical ventilation.
- 6. Subject has abnormal liver test parameters: AST or ALT ≥5 x ULN and/or total bilirubin >2.5 x ULN.

Note: Subjects with unconjugated hyperbilirubinemia (< 7mg/dL) with a diagnosis of Gilbert's disease **are not excluded**.

- 7. Subject has a grade II-IV acute or extensive chronic graft-versus-host disease (GvHD).
- 8. Subject has renal failure requiring dialysis.
- 9. Subject has a prolonged QTcF interval (Fridericia's correction: QTc= QT/(RR)^{0.33}) >480 ms for females and prolonged QTcF interval (Fridericia's correction: QTc= QT/(RR)^{0.33})
 >450 ms for males, on the baseline ECG or other abnormalities deemed clinically significant by the investigator that would put the subject at unacceptable risk for participation in the study.
- 10. Subject has any other condition including history of conditions or medications that may increase the risk for QTc prolongation, or laboratory abnormality that, in the judgment of the investigator, would put the subject at unacceptable risk for participation in the study or may interfere with the assessments included in the study.
- 11. Subject has a known hypersensitivity to SCY-078 and/or voriconazole or any of the components of the formulations.
- 12. Subject has participated in any other investigational study (except open-label studies including approved chemotherapy agents) within at least 28 days or 5.5 half-lives of the investigational product (whichever is longer) before signing the ICF.
- 13. Subject has received prior treatment with SCY-078 in a previous trial.
- 14. Subject is an employee of SCYNEXIS, Inc., the investigator or the Contract Research Organization (CRO) involved in the study, or is an immediate family member (partner, offspring, parent, sibling, or sibling's offspring) of an employee involved in the study.
- 15. Subject is unlikely to comply with protocol requirements.

12.3 Discontinuation Criteria

A subject may be discontinued from the study or study drug for any of the following reasons:

- Withdrawal of consent;
- Investigator or Sponsor decision that withdrawal is in the subject's best interest;
- Lack of efficacy, defined as deterioration of the clinical condition or delayed response requiring, in the opinion of the investigator, alternative antifungal therapy;

- Occurrence of an AE that, in the opinion of the investigator, warrants discontinuation of the subject from the study drug;
- Pregnancy;
- Lost to follow up (every attempt should be made to contact the subject).

The reason for a subject's discontinuation of treatment or withdrawal from the study will be clearly documented in the source documents and on the electronic case report form (eCRF). All EoT procedures should be performed for subjects who discontinue from study treatment before the EoT visit.

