15.3 Subject Enrollment and Assignment of Subject Number

At Baseline/Treatment Day 1, all subjects who have signed an ICF will receive an 8-digit subject identification (ID) number that will be composed of a 3-digit study number (206) and a 2-digit site number followed by a 3-digit sequentially assigned subject number starting at 001. Subject numbers will be sequentially assigned by the database upon entry by the site. For instance, if site 01 enters the first subject in the database, the subject ID will be 206-01-001. The second subject entered in the database will get the subject number 002 as entered by any site, so that if site 02 enters the second subject, the subject ID will be 206-02-002. This number will be unique to each subject and will be used to identify the subject throughout the study.

Subjects who are screen failures or who are not eligible for enrolment will be recorded as such in the subject screening log. The subject numbers assigned to eligible subjects will be recorded in the eCRF. Only one subject number will be assigned to each eligible subject.

For subjects who signed an ICF (i.e., are assigned a subject number) but were NOT randomized because they did not meet all of the inclusion/exclusion criteria or other reason, selected Screening visit pages of the eCRF will be completed. The criteria that were not met for enrolment will also be documented in the eCRF.

All eligible subjects must be approved by the Sponsor for enrollment. When available, the antifungal therapy administered and Survival status at Days 42 and 84 will be collected for subjects who signed the ICF but were NOT randomized.

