17.5 Pregnancy

Female subjects who become pregnant should be immediately discontinued from the study and followed up to determine the outcome of the pregnancy. The pregnancy must be reported to the Sponsor within 24 hours of the site becoming aware of the pregnancy. If the pregnancy ends for any reason before the anticipated date, the investigator should notify the Sponsor. At the completion of the pregnancy, the investigator will document the outcome of the pregnancy. If the outcome of the pregnancy meets the criteria for immediate classification as an SAE (i.e., postpartum complication, spontaneous abortion, stillbirth, neonatal death or congenital anomaly), the investigator should follow the procedures for reporting an SAE.

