8.2.2. Overall Survival

Overall survival is defined as the time from randomization to time of death up to Day 84.

Subjects with death will be censored at Day 84, date of withdrawal or date of last follow up whichever comes earliest.

Overall survival will be expressed in days and calculated using the formula:

$$\text{Overall Survival} = \text{Date of Death/Censoring} - \text{Date of Randomization.}$$

The number and percentage of subjects with events and censored will be summarized.

The Kaplan-Meier method will be used to estimate the distribution of overall survival for each treatment group. The 25th percentile, median and 75th percentile overall survival and their 95% CIs will be presented. In addition, the overall survival (%) at Day 42 and Day 84 and their 95% CIs will also be presented.

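### Protocol 12.3 does not separate stopping study drug from leaving the study, and SAP 8.2.2 censors at withdrawal, so survival follow-up can end because a subject deteriorated

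*Protocol*

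**What the plan says.** Protocol 12.3 uses one list for two different events: "A subject may be discontinued from the study or study drug for any of the following reasons". One reason on it is "Lack of efficacy, defined as deterioration of the clinical condition or delayed response requiring, in the opinion of the investigator, alternative antifungal therapy", which is not tied to study drug alone. The adverse-event reason is worded more narrowly, as an event that "warrants discontinuation of the subject from the study drug". The only assessment that 12.3 requires afterwards is this: "All EoT procedures should be performed for subjects who discontinue from study treatment before the EoT visit". It mentions neither the 6-Week Follow-Up nor the Day 42 and Day 84 contacts.

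Protocol 17.5 goes straight to the study level: "Female subjects who become pregnant should be immediately discontinued from the study and followed up to determine the outcome of the pregnancy".

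Protocol 15.23 has survival determined at Days 42 and 84 for randomized subjects, by visit or telephone, with no exception for those who stopped early. It does not mention subjects who have been discontinued from the study.

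SAP 8.2.2 censors overall survival at Day 84, "date of withdrawal or date of last follow up whichever comes earliest". As printed, the sentence applies this to subjects who died, where it must mean those who did not. SAP 8.2.3 counts deaths by Days 42 and 84 and gives no rule for a subject whose vital status is unknown.

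**The concern.** Deaths are part of the primary endpoint (Protocol 10.1). All-cause mortality at Days 42 and 84 and overall survival are secondary endpoints (10.2). A subject who is deteriorating and needs another antifungal is at higher risk of death than one who is responding. If that subject can be recorded as discontinued from the study, and the contacts then stop, a later death is neither counted in 8.2.3 nor observed in 8.2.2. Censoring of this kind depends on prognosis, so the Kaplan-Meier assumption that censored subjects resemble those still at risk fails. Mortality is then understated, and more so in whichever arm loses more such subjects. With about 11 subjects per arm, a single case matters.

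**Working it through.** **Tracing the text.** Take a randomized subject who deteriorates, needs another antifungal, and is recorded as discontinued from the study.

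- Protocol 12.3 permits this and asks for the EoT procedures.
- Protocol 15.23 would have survival checked at Days 42 and 84, because the subject was randomized. It does not say that this continues after study discontinuation.
- Protocol 11.1.1.5 schedules a visit 6 weeks after EoT, again without saying whether it applies to someone who has left the study.
- Protocol 17.11 follows reported AEs and SAEs to an outcome whether or not the subject is still in the study. Events that first arise afterwards are not secured by that sentence.
- Protocol 14.2 does not permit other antifungals up to the 6-Week Follow-Up, yet this subject needs one by definition. Protocol 9.3 has an objective on additional antifungal treatment until Week 6 after EoT. How such a subject is to be classified is not stated, and the passages must be reconciled.
- SAP 8.2.2 stops the survival clock at withdrawal if that precedes Day 84 and last follow-up. It does not say whether a death learned of later counts, and it discards any later time known to be alive.
- SAP 8.2.3 has no rule for unknown vital status. The missing-data rules in SAP 6.3 and 8.1 concern response, not survival.

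So 12.3 and 17.5 allow study discontinuation, 15.23 implies continued survival contact, and SAP 8.2.2 expects survival time to end at withdrawal. Nothing reconciles the three.

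**Illustrating the size.** There is no figure in the plan to reproduce: Protocol 19.1 defines no formal sample size, and no withdrawal rate is given.

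Inputs:
- Arm size: 11 (SAP 3.4) and the planned 30 (Protocol 11.2).
- Assumed mortality: about 27%, from the 6-week rate on monotherapy in the large combination trial cited in Protocol 8.1 (39/142 = 27.5%). This gives 11 × 0.275 = 3.0, so 3 deaths in 11, and 30 × 0.275 = 8.25, so 8 in 30.
- k: the number of subjects withdrawn who later die unrecorded, assumed to be 1 or 2.

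Shift from one unrecorded death with the full arm as denominator: 1/11 = 9.1 points; 1/30 = 3.3 points.

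Crude mortality is (d − k)/N. Kaplan-Meier mortality is (d − k)/(N − k) if the withdrawals precede the first observed death.

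| N | True | k | Crude | Kaplan-Meier, early withdrawal |
|---|---|---|---|---|
| 11 | 3/11 = 27.3% | 1 | 2/11 = 18.2% | 2/10 = 20.0% |
| 11 | 27.3% | 2 | 1/11 = 9.1% | 1/9 = 11.1% |
| 30 | 8/30 = 26.7% | 1 | 7/30 = 23.3% | 7/29 = 24.1% |
| 30 | 26.7% | 2 | 6/30 = 20.0% | 6/28 = 21.4% |

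Early withdrawal is the mildest case for Kaplan-Meier. If the subject withdraws after both observed deaths, the estimate is 2/11 = 18.2%, the same as the crude rate.

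SAP 8.2.3 does not state its denominator. Under the general convention in SAP 13.2.5.2, which uses subjects with an observation, an unknown status would leave the denominator and the result would be 2/10 = 20.0%. The understatement is then 27.3 − 20.0 = 7.3 points instead of 9.1.

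For scale, the whole 6-week difference in the cited trial was 26/135 − 39/142 = 19.3% − 27.5% = −8.2 points.

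**The case against.** The strongest reply is that the plan intends follow-up to continue. Section 15.23 is unconditional for randomized subjects, and Table 5 sets the Day 42 and Day 84 contacts without tying them to being on treatment. The radiological definition expects EoT before Day 42 in some subjects, so off-treatment contacts are part of the design. Early stoppers have EoT procedures, and 11.1.1.5 places a visit 6 weeks after EoT. The antifungal-use objective in 9.3, and the recording of antifungals after EoT in 14.1, make little sense if those subjects routinely leave. SAP 7.1 tabulates treatment and study discontinuation separately, and SAP 8.2.3 sets no cut-off for deaths at withdrawal.

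Most of this stands. It shows that follow-up is not ended by rule, and that subjects who merely stop drug are probably meant to stay. It does not cover a subject whom a site records as discontinued from the study, for which 12.3 gives lack of efficacy as an accepted reason and SAP 8.2.2 accepts withdrawal as the end of survival time.

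Three stronger readings are tempting, and the documents do not support them.

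- A reader might infer that randomized treatment failures are followed less completely than screen failures, because Protocol 15.3 says "Survival status at Days 42 and 84 will be collected for subjects who signed the ICF but were NOT randomized". That sentence is qualified at its start as applying only when the information is available, whereas 15.23 states survival for randomized subjects outright.
- A reader might infer that subjects discontinued for an AE or pregnancy are those most likely to die. The AE reason speaks of study drug only, and nothing links pregnancy to mortality here. The argument about informative loss rests on lack of efficacy.
- A reader might infer that safety follow-up lapses altogether. Section 17.11 rules that out for reported events; only newly arising ones could be missed.

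It is also fair to say that the figures are arithmetic for hypothetical subjects in a descriptive study, and that the 8.2-point comparison comes from an analysis of 277 patients. It gives scale and is not a benchmark for this trial.

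**Conclusion.** The concern holds as an unresolved gap between 12.3, 17.5, 15.23 and SAP 8.2.2. The stated rules permit survival follow-up to end because a subject deteriorated, and they allow known survival time after withdrawal to be discarded. They do not require either. Loss of that kind is informative and would understate mortality.

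The illustrated size is up to 9.1 points per unrecorded death at 11 per arm and 3.3 points at 30 per arm. It rests on an assumed mortality near 27% and one such subject in the arm. Whether any exist among the 22 cannot be told from the documents. Because retrieval is cheap and deaths enter the primary endpoint, this merits a change and not only a clarifying note.

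**What to change.** 1. In Protocol 12.3 and 17.5, separate stopping study drug from leaving the study and reconcile both with 15.23. State that subjects who stop study drug for any reason remain in the 6-Week Follow-Up, AE collection and the Day 42 and Day 84 contacts, unless they withdraw consent for follow-up or are lost. Leave the reasons for stopping treatment as they are, including the investigator or sponsor decision.
2. For the 22 randomized subjects, obtain Day 42 and Day 84 vital status for those who were discontinued, where consent allows.
3. In SAP 8.2.2, count any known death up to Day 84 as an event. Censor subjects without a known death at the last date known alive up to Day 84, not at the date of withdrawal. Correct the censoring sentence so that it refers to subjects without death.
4. In SAP 8.2.3, report by arm how many subjects have unknown vital status at Days 42 and 84, and add a sensitivity analysis that counts them as deaths. With 2 known deaths and 1 unknown in 11, for example, the display would show 18.2% with the unknown counted as alive and 27.3% with it counted as a death.

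The cost is a few contacts of a type already planned, plus one extra analysis. Enrolment has stopped at 22 (SAP 11 and 12), so the immediate gain lies in items 2 to 4. Item 1 mainly serves any subject still in follow-up and the later studies that this trial is meant to inform.

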12.4 Replacement of Dropouts

Subjects who discontinue early from treatment will not be replaced.

13.0 Study Treatments

13.1 Study Treatment Groups

13.1.1 Description of Study Groups

All eligible subjects will be randomized in a 1:1 ratio to one of the two study treatment groups and will receive treatment for a recommended minimum of 6 weeks and a maximum of 13 weeks.

Once randomized, the subjects will receive either voriconazole plus SCY-078 or voriconazole plus matching SCY-078 placebo for the entire duration of the antifungal treatment, until they reach EoT or a discontinuation occurs.

Voriconazole + SCY-078

- Either IV voriconazole (loading dose of 6 mg/kg BID on Day 1 followed by maintenance dose of 4 mg/kg BID from Day 2 onwards) OR oral voriconazole (loading dose of 400 mg BID on Day 1 followed by maintenance dose of 200 mg BID from Day 2 onwards). For subjects weighing <40 kg, the loading and maintenance dose of oral voriconazole will be determined per label instructions.
 PLUS
- Oral **SCY-078** (loading dose of 500 mg [2 tablets of 250 mg] BID on Days 1 and 2 followed by maintenance dose of 500 mg [2 tablets of 250 mg] QD from Day 3 onwards). After the first 10 randomized subjects have been treated with the coadministration therapy for at least 7 days, an interim PK analysis will be conducted. Based on the data from this analysis, the oral **SCY-078** dose for subjects subsequently randomized may be increased up to a loading dose of 750 mg (3 tablets of 250 mg) BID on Days 1 and 2

followed by a maintenance dose of 750 mg (3 tablets of 250 mg]) QD from Day 3 onwards.

Voriconazole + SCY-078 Placebo

- Either IV voriconazole (loading dose of 6 mg/kg BID on Day 1 followed by maintenance dose of 4 mg/kg BID from Day 2 onwards) OR oral voriconazole (loading dose of 400 mg BID on Day 1 followed by maintenance dose of 200 mg BID from Day 2 onwards). For subjects weighing <40 kg, the loading and maintenance dose of oral voriconazole will be determined per label instructions.
 PLUS
- Placebo matching oral SCY-078
 - Subjects randomized prior to the interim PK analysis: loading dose of 2 tablets given BID on Days 1 and 2 followed by maintenance dose of 2 tablets given QD from Day 3 onwards.
 - Subjects subsequently randomized (depending on interim PK analysis): loading dose of up to 3 tablets given BID on Days 1 and 2 followed by maintenance dose of up to 3 tablets given QD from Day 3 onwards

Subjects will receive the administration of voriconazole as per label instructions and local standard practice. The individual dose of voriconazole may be adjusted by the investigator according to results from standard-of-care voriconazole drug monitoring evaluations. Subjects should be instructed to take oral voriconazole 1 hour before or after a meal, every 12 hours. The dose of SCY-078 will not be adjusted for a particular subject. Subjects will be instructed to take the oral SCY-078 preferably with meal, twice a day (BID) approximately 12 hours apart the first 2 days (loading dose) and once daily (QD) subsequently (maintenance dose). The dose of SCY-078 may be adjusted for subjects who are randomized after the interim PK analysis. Until a decision to adjust the dose is made based on data from this analysis, subjects will continue receiving SCY-078 500 mg doses.

See Section 13.1.4 for voriconazole dosing recommendations. For additional information on voriconazole, please refer to Section 22.2 (Appendix B: Voriconazole Label). A summary of the study treatment groups is provided in Table 3.

Table 3 Study Treatment Groups First 20 Randomized Subjects ^a						
Drugs	Voricon	azole +	SCY-078	Voricon	azole +	SCY-078 matching placebo
Route	IV ^b	Oral	Oral	IV ^b	Oral	Oral
Loading dose	6 mg/kg	400 mg ^c	500 mg	6 mg/kg	400 mg ^c	Placebo
	BID	BID	BID	BID	BID	BID
	(Day 1)	(Day 1)	(Days 1 & 2)	(Day 1)	(Day 1)	(Days 1 & 2)
Maintenance	4 mg/kg	200 mg ^d	500 mg	4 mg/kg	200 mg ^d	Placebo

dose	BID	BID	QD	BID	BID	QD
	(Day 2 onwards)	(Day 2 onwards)	(Day 3 onwards)	(Day 2 onwards)	(Day 2 onwards)	(Day 3 onwards)
	Subsequent Su	ıbjects (depend	ing on interin	1 pharmacol	kinetic anal	ysis)
Drugs	Voricon	azole +	SCY-078	Voricon	azole +	SCY-078 matching placebo
Route	IV ^b	Oral	Oral	IV ^b	Oral	Oral
Loading dose	6 mg/kg	400 mg ^c	750 mg	6 mg/kg	400 mg ^c	Placebo
	BID	BID	BID	BID	BID	BID
	(Day 1)	(Day 1)	(Days 1 &	(Day 1)	(Day 1)	(Days 1 & 2)
36.14	4 1	b 000	2)	4 1	200 d	D1 1
Maintenance	4 mg/kg	200 mg"	/50 mg	4 mg/kg	200 mg ^a	Placebo
dose	BID	BID	QD	BID	BID	QD
	(Day 2 onwards)	(Day 2 onwards)	(Day 3 onwards)	(Day 2 onwards)	(Day 2 onwards)	(Day 3 onwards)

Abbreviations: BID: twice a day; IV: intravenous

a: The 500 mg dose will be administered to the first 20 randomized subjects. An interim pharmacokinetic analysis will be conducted and, based on data from this analysis, the SCY-078 dose may be increased up to the 750 mg dose for subjects subsequently randomized.

b: IV voriconazole should be infused over 1 to 2 hours (rate not to exceed 3 mg/kg/h). It should not be administered as an IV bolus injection.

c: Administering an oral voriconazole loading dose is only recommended in subjects who cannot tolerate IV voriconazole due to potential renal adverse effects.

d: For subjects who take oral voriconazole and weigh <40 kg, the loading and maintenance dose will be per label instructions.

